4.1. Visit 1 (Day 0)

At the screening visit, the following procedures will be undertaken:

- Subject is fully informed about the study and gives written agreement to study participation in the form of a signed informed consent form (refer to [Section 4.1.1](#))
- Assess eligibility (refer to [inclusion/exclusion criteria](#))
- Review of medications
- Medical history including history of constipation (ROME criteria – See [Inclusion #2](#))
- Physical examination
- Vital signs, including assessment of orthostatic hypotension (while seated and after standing for a minimum of 2 minutes) including height and bodyweight, pulse and temperature
- A 12-lead ECG will be performed by qualified, trained site personnel. ECG output must be reviewed by a physician investigator. Any clinically significant cardiac abnormalities identified on the ECG should disqualify a subject. Data from the ECG will be collected in the eCRF.
- Urine pregnancy test (if applicable)
- Blood and urine samples will be collected for testing at a central laboratory, as shown below.

Chemistry: alkaline phosphatase, ALT, anion gap, AST, bicarbonate, blood urea nitrogen (BUN), calcium, chloride, creatine kinase, creatinine, eGFR, GGT, HCG, inorganic phosphate, magnesium, osmolality, potassium, sodium, uric acid. CK-MB will be tested in samples where the CK value is greater than 2.5 times the upper normal limit.

Hematology: hematocrit, hemoglobin, platelets count, red blood cell count, white blood cell count (and differentials)

Urinalysis: including electrolytes (sodium, potassium, magnesium, calcium), microscopic analysis, urine osmolality

Subjects with clinically significant laboratory abnormalities, deemed as a potential safety issue by the Investigator, may be discontinued at the Investigator's discretion.

If the subject is eligible for the study, assign a subject number.

Braintree Laboratories, Inc.
Protocol Number BLI400-303

Confidential

- Subjects will complete the Patient Assessment of Constipation Quality of Life questionnaire (PAC-QOL, refer to [Appendix A](#)) and the Patient Assessment of Constipation Symptom questionnaire (PAC-SYM, refer to [Appendix B](#))
- Dispense 2 bottles of BLI400
- Dispense rescue bisacodyl. Subjects will be allowed to take 5 – 10mg of bisacodyl if they are experiencing severe discomfort due to their constipation, or have not had a BM in 4 days.
- Instruct subject to maintain their normal dietary habits during study participation

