5. ADVERSE EVENTS

5.1. Adverse Event Definition and Reporting

An Adverse Event (AE) is any untoward medical occurrence associated with the use of a drug in humans, whether or not considered drug related. An AE can therefore be any unfavorable and unintended sign (including a clinically significant abnormal laboratory finding), symptom, or disease temporally associated with the use of a medicinal (investigational) product.

Adverse event collection will coincide with the subject providing informed consent to participate in the study and will conclude with the end of study participation at Day 374 Follow-up Call. Diarrhea should be reported as an adverse event if a subject has more than 3 watery stools per day. Subjects with clinically significant laboratory results at Visit 6 which are classified by the Investigator as adverse events should return for a repeat blood draw. Subjects will be instructed to report promptly adverse events to the Investigator. The Investigator will record date/time of report, date/time of onset, description of the adverse event, severity of adverse event, action(s) taken regarding treatment of the event, action(s) taken regarding study participation, duration of adverse event, and the Investigator's assessment of relationship of adverse event to study treatment.

The Investigator should assess the severity of each adverse event using the following categories:

Grade	Severity	Description
1	Mild	Barely noticeable, does not influence functioning Causing no limitations of usual activities
2	Moderate	Makes participant uncomfortable, influences functioning Causing some limitations of usual activities
3	Severe	Severe discomfort, treatment needed Severe and undesirable, causing inability to carry out usual activities
4	Life threatening	Immediate risk of death Life threatening or disabling
5	Fatal	Causes death of the participant

Braintree Laboratories, Inc.
Protocol Number BLI400-303

Confidential

The Investigator should assess the relationship to study drug for each adverse event using the following categories:

Categories of Attribution:	Description
UNRELATED	There is no evidence of any causal relationship.
POSSIBLE	There is some evidence to suggest a causal relationship (e.g., the event occurred within a reasonable time after administration of the trial medication). However, the influence of other factors may have contributed to the event (e.g., the patient's clinical condition, other concomitant events).

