9. DATA ANALYSIS

9.1. Sample Size

Consistent with *ICH E1A Guideline for Industry, the Extent of Population Exposure to Assess Clinical Safety: for Drugs Intended for Long-term Treatment of Non-Life-Threatening Conditions (March 1995)*, 300 subjects will be treated with BLI400 for 12 months. This will allow for detection of adverse events that may increase in frequency or severity over time.

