9.3.2. Safety Analyses

Analysis of safety will be performed using the modified Intent to Treat population (see [Section 9.4](#)).

Adverse Events

Adverse Events will be coded using the MedDRA classification to provide a preferred term and primary system organ class for each event. Proportions of subjects with adverse events will be presented for the overall study population, and each demographic subgroup (age, gender and race). Tables of AEs will be presented by system organ class and preferred term, and include overall totals for AEs within each system organ class. Counting will be done by subject and not by event. A table of counts and percentages will also be made of those subjects with SAEs or AEs which led to withdrawal from the study.

Treatment-emergent AEs are defined as adverse events that had an onset day and time on or after the day and time of the first dose of study drug until the Day 374 Follow-up Call. Adverse Events having missing onset dates will be considered as treatment emergent.

The difference in adverse event rates between study periods will be tested by Chi-Square or Fisher's exact test with 95% confidence intervals.

Laboratory Parameters

Summary statistics (i.e., mean, minimum, maximum, standard deviation, and number of subjects) will be presented for each laboratory parameter at each visit. Laboratory data will be summarized for the overall population and the elderly and non-elderly subgroups. When calculating the summary statistics only, the last observation within a visit window will be used if there are multiple observations. Changes from baseline (Visit 1) will be presented in a similar format. An additional listing will be provided of those subjects who have clinically significant laboratory values. The data will also be presented as shift tables and clinically significant abnormalities will be examined.

Results of laboratory tests for the change from baseline (Visit 1) and group differences will be tested using ANOVA.

Vital Signs

Summary statistics (i.e., mean, minimum, maximum, standard deviation, and number of subjects) will be presented for each vital sign at each visit and compared to the values obtained at Visit 1. When calculating the summary statistics only, the last observation within a visit window will be used if there are multiple observations. The data will also be presented as shift tables and clinically significant abnormalities will be examined.

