4.2.2. Visit 2 (Month 2) +/- 4 days

Subjects will continue to take BLI400 daily and will return to the clinic for Visit 2 (Day 60). Vital signs (see section 4.1 for details) and ECGs will be recorded. Study personnel will weigh returned bottles and count rescue bisacodyl for accountability purposes. Subjects will be queried for any adverse events or changes to their concomitant medications. Subjects will complete the PAC-QOL and PAC-SYM questionnaires. Samples for chemistry, hematology and urinalysis will be repeated as outlined in Section 4.1. Subjects will be dispensed 2 new bottles of study medication. Subjects will be instructed to return all bottles and bisacodyl at the next follow up visit.

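### Seated and standing readings are taken to assess orthostatic hypotension, but section 9.3.2 defines no standing-minus-seated change, no criterion for a drop and no count of subjects, so drops confined to a minority may be missed and their frequency is not planned to be reported

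*Combined protocol and SAP*

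**What the plan says.** Section 4.1 (Visit 1) specifies "Vital signs, including assessment of orthostatic hypotension (while seated and after standing for a minimum of 2 minutes", together with height, weight, pulse and temperature. The footnote to the schedule in section 4.3 names blood pressure and pulse in both positions, and vital signs are marked at Visits 1 to 6. The text for each later visit points back to section 4.1; for Visit 2 it reads "Vital signs (see section 4.1 for details) and ECGs will be recorded".

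Section 9.2 includes vital signs among the safety data to be analysed. Under Vital Signs in section 9.3.2, the mean, minimum, maximum, SD and number of subjects "will be presented for each vital sign at each visit and compared to the values obtained at Visit 1". Where a visit window holds several observations, only the latest enters the summary statistics. The paragraph ends: "The data will also be presented as shift tables and clinically significant abnormalities will be examined".

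Nothing in section 9.3.2 says how seated and standing values are labelled or kept apart. It gives no criterion for an abnormality in vital signs, and no split by elderly status for them. The laboratory paragraph has that split, and also this: "An additional listing will be provided of those subjects who have clinically significant laboratory values". There is no matching listing for vital signs. The two copies of the protocol in the combined document agree on all of this.

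**The concern.** Orthostatic hypotension is a property of a pair of readings in one subject. The measurement is designed around that pair, but the analysis is written reading by reading. As an invented example, a subject at 138 mmHg seated and 110 mmHg standing falls by 28 mmHg, yet both values could lie inside whatever normal range the shift tables use (the plan states none). Such a subject might not shift category and would barely affect a mean.

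Safety is the trial's only objective. The product is an osmotic laxative taken for a year, sections 3.4 and 4.2.1 anticipate persistent diarrhea or loose stools, and section 3.2 plans about 100 subjects aged 65 or older. Fluid loss with a fall in standing pressure is a plausible thing to look for, and the sites will already have collected the data. What is at stake is whether the report can say how many subjects had such a fall, and at which visits.

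**Working it through.** The plan has no figure to reproduce here: it gives no blood pressure mean, SD, correlation or threshold. The 300 in section 9.1 ("300 subjects will be treated with BLI400 for 12 months") rests on guideline exposure, not on a power formula, and is used below only as a scale. **Every blood pressure value, proportion and threshold below is an assumption for illustration.**

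1. *What separate summaries do give.* When the same subjects have both readings, mean(standing − seated) = mean(standing) − mean(seated). In one simulated set of 300, the seated mean was 123.5 and the standing mean 121.5 mmHg. The difference of −2.0 agrees, to rounding, with the mean paired change of −1.92. The average drop is therefore recoverable.

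2. *What they do not give.* Keep the same 300 seated and 300 standing values, but shuffle which standing value belongs to which subject:

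| | Seated mean / SD / min / max | Standing mean / SD / min / max | Subjects falling ≥ 20 mmHg |
|---|---|---|---|
| Original pairing | 123.5 / 13.8 / 84.3 / 171.5 | 121.5 / 15.1 / 80.8 / 173.9 | 0 |
| Re-paired | 123.5 / 13.8 / 84.3 / 171.5 | 121.5 / 15.1 / 80.8 / 173.9 | 55 |

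 Every planned summary statistic is identical, but the count differs by 55 of 300. Full shuffling is an extreme; it shows that the summaries do not determine the count.

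3. *The same point by formula.* With SD 15 in each position, correlation ρ and mean change −2, SD of the change = 15 × √(2(1 − ρ)). The expected count is 300 × Φ((−20 + 2) / SD of the change):

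| ρ | SD of change | Expected count of 300 |
|---|---|---|
| 0 | 21.21 | 59.4 |
| 0.5 | 15.0 | 34.5 |
| 0.8 | 9.49 | 8.7 |
| 0.9 | 6.71 | 1.1 |
| 0.95 | 4.74 | 0.0 |

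 Separate summaries say nothing about ρ, and the answer turns on ρ.

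4. *How far a minority moves the mean.* If a fraction f has an extra drop D, the standing mean moves by f × D. For f from 2% to 10% (6 to 30 of 300) and D from 10 to 30 mmHg, the shift runs from 0.02 × 10 = 0.2 to 0.10 × 30 = 3.0 mmHg, or 0.01 to 0.20 of an SD of 15. The standing SD rises from 15 to between 15.07 and 17.49. For f = 5% (15 subjects) and D = 25, the shift is 0.05 × 25 = 1.25 mmHg.

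5. *Against the standard error.* With SD 10 to 15 and n = 300, SE = 10/√300 = 0.58 to 15/√300 = 0.87 mmHg. The 1.25 mmHg shift is 1.4 to 2.2 SE. Such a shift might or might not stand out in a mean. If it did, the mean still could not say whether 15 subjects fell by 25 mmHg or all 300 fell by 1.25.

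**The case against.** A reader might infer from the reading-by-reading tables that an orthostatic drop would go unseen, or that the planned method cannot address the question at all. The documents do not support that, for four reasons.

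- Section 9.3.2 plans an examination of clinically significant abnormalities in vital signs. That is a possible subject-level route, although it has no criteria and no stated output.
- Section 5.1 defines adverse events broadly: "An AE can therefore be any unfavorable and unintended sign (including a clinically significant abnormal laboratory finding), symptom, or disease". A fall that the investigator judges untoward can be recorded, and adverse events are counted by subject, overall and by age, gender and race.
- The plan is silent on how the two positions are handled. That they are summarised separately, with no paired change, is an inference, and the orthostatic assessment is listed within vital signs.
- If they are summarised separately, the mean drop follows by subtraction, so a large drop shared by most subjects would show.

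It can also be said that the summary sheet's primary endpoint does not list vital signs, that section 1 describes adverse events as mainly gastrointestinal, and that the table could be produced later because the data are held.

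All of this stands as a limit on the claim. It does not close the gap. Adverse event capture depends on symptoms or judgement, so it does not yield a frequency from the systematic readings. An examination without criteria commits the sponsor to no count. Section 9.2 does list vital signs for safety analysis. A criterion chosen after open-label data have been seen is worth less than one fixed beforehand.

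**Conclusion.** The point holds as a mismatch between a measurement and its analysis. The readings are taken for a within-subject purpose, and section 9.3.2 commits to no within-subject change, no criterion and no count. The number of subjects with a drop cannot be recovered from the planned summary statistics. On the assumed values (SD 15, mean change −2, illustrative 20 mmHg), the same kind of summaries is compatible with anything from 0 to about 59 of 300 subjects. A drop confined to 2% to 10% of subjects moves the standing mean by only 0.2 to 3.0 mmHg. Drops in a minority may therefore be missed, and their frequency is not planned to be reported.

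The conclusion does not extend to saying that drops would be invisible, or that there is any signal of orthostatic harm; the documents report none. The 2% to 10%, 5%, 10 to 30 and 25 mmHg, the SD of 10 to 15 mmHg and the 20 mmHg cut are illustrations, not figures from the plan. The structural result, that separate summaries do not fix the count, does not depend on them.

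**What to change.** Amend the Vital Signs paragraph of section 9.3.2 as follows.

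- Keep seated and standing readings as separate variables, so that the rule using the last observation in a visit window cannot discard one of the pair.
- Derive standing minus seated for systolic pressure, diastolic pressure and pulse, per subject and visit. Summarise these and their change from Visit 1.
- Report n (%) of subjects at each visit, including Visit 1, who meet a criterion for a drop that the sponsor fixes in advance. Because the study is open-label, that should be before the vital-sign data are reviewed, not merely before database lock. No numeric criterion is proposed here, because the documents give none.
- Add a listing of those subjects, and present the results overall and for elderly and non-elderly subjects, as is already planned for laboratory data.
- State that any count of subjects with a new drop at any later visit is descriptive. There is no control arm, and five post-baseline visits set against one baseline reading give repeated chances to cross a threshold.

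The cost is one derived variable (applied to three readings), one extra table and its listing. Visits, procedures and sample size do not change.

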12.3.	AMENDMENTS TO THE PROTOCOL	29
12.4.	DATA RECORDS.....	29
13.	PUBLICATION AND AGREEMENT	29
14.	INVESTIGATORS AGREEMENT	30
15.	REFERENCES	31
16.	APPENDIX A	32
	APPENDIX B	35

Braintree Laboratories, Inc.
Protocol Number BLI400-303

Confidential

CLINICAL PROTOCOL SUMMARY SHEET**STUDY TITLE:**

An Open Label Study of Chronic Use of BLI400 Laxative in Constipated Adults

PROTOCOL: BLI400-303**VERSION DATE:** 4-13-2016**IND NUMBER:** 118,906**OBJECTIVE:**

To evaluate the safety of chronic use of BLI400 Laxative in constipated adults.

STUDY DESIGN:

This is an open-label, multi-center study in constipated outpatients.

SUBJECTS:

Approximately 300 male or female adult subjects with a history of constipation will be enrolled in this study (including approximately 100 elderly subjects).

STUDY MEDICATIONS:

BLI400 Laxative (21 grams of Lactitol Monohydrate, NF)

DURATION OF TREATMENT

Subjects will take BLI400 laxative daily for 12 months (52 weeks). Participation in this study will last for approximately 54 weeks, including the 14 day follow up telephone call.

PRIMARY ENDPOINT

Safety will be analyzed through the use of adverse event and ECG data, and the comparison of chemistry, hematology, and urinalysis values as measured at baseline and at specific time points throughout the study.

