9.2. Parameters to be Analyzed

The primary objective of this study is to investigate the safety of BLI400 used chronically for 12 months in subjects with constipation. Safety will be analyzed using ECG, vital signs, chemistry, hematology and urinalysis and adverse event data. Treatment emergent adverse event rates will be descriptively presented by preferred term, severity, and relationship to treatment.

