ECG variables will be tabulated and presented for data collected at each visit. Data will be tabulated and summarized with descriptive statistics (N, mean, SD, CV%, SEM, minimum, and maximum) for each of the ECG variables. The differences in ECG variables between Visit 1 (Baseline), Visit 2 and Visit 6 will be tested using ANOVA.

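### ECG is summarised only at visit level (descriptive statistics and ANOVA), so the number of subjects with a large change from their own baseline would not be reported

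*Combined protocol and SAP*

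**What the plan says.** The Primary Endpoint entry of the Clinical Protocol Summary Sheet reads "Safety will be analyzed through the use of adverse event and ECG data, and the comparison of chemistry, hematology, and urinalysis values". That names five data types: adverse events, ECG, chemistry, hematology and urinalysis. Section 9.2 adds vital signs as a sixth and lists them apart from ECG: "Safety will be analyzed using ECG, vital signs, chemistry, hematology and urinalysis and adverse event data".

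The ECG plan is one short paragraph in Section 9.3.2, identical in both copies of the protocol in the file. It opens with "ECG variables will be tabulated and presented for data collected at each visit" and continues "Data will be tabulated and summarized with descriptive statistics (N, mean, SD, CV%, SEM, minimum, and maximum) for each of the ECG variables". The test is "The differences in ECG variables between Visit 1 (Baseline), Visit 2 and Visit 6 will be tested using ANOVA". The model, the handling of repeated measures and the alpha level are not given.

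Under Laboratory Parameters and again under Vital Signs, the same section says "The data will also be presented as shift tables and clinically significant abnormalities will be examined". For laboratory data it also plans change-from-baseline summaries and a listing: "An additional listing will be provided of those subjects who have clinically significant laboratory values". The ECG paragraph has no counterpart to any of these.

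**The concern.** Safety is the study's only objective, and ECG is named in the primary endpoint. Vital signs are not named there, yet they get shift tables and a review of clinically significant abnormalities, and ECG does not.

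Summaries of visit values and a comparison of visit means describe the group. They do not say how many subjects moved far from their own starting point.

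The omitted count would be easy to interpret here. Exclusion criterion 11 and Section 4.1 keep out subjects with a clinically significant cardiac abnormality on the Visit 1 ECG, so such a finding at Visit 2 or 6 should be new since baseline, which makes it informative even without a control arm. The Introduction reports electrolyte changes in animals and, in one human study, plasma potassium that rose but stayed within the normal range. About 100 of the 300 subjects are to be elderly. A reader of the study report will want to know how many subjects changed, and the plan as written produces no table that answers this.

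**Working it through.** **Side-by-side reading of Section 9.3.2**

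| Planned item | Laboratory | Vital signs | ECG |
|---|---|---|---|
| Named in primary endpoint | yes | no | yes |
| Visit-level summary with min and max | yes | yes | yes, plus CV% and SEM |
| Comparison with Visit 1 | change-from-baseline summaries and ANOVA | visit values compared with Visit 1 | ANOVA of Visits 1, 2 and 6 only |
| Shift tables | yes | yes | no |
| Review of clinically significant abnormalities | yes | yes | no |
| Listing of affected subjects | yes | no | no |

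The vital-signs sentence cannot be read as covering ECG. Section 9.2 treats the two as separate data types, and the ECG paragraph sets out its own statistics.

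**Plan's own figure.** Section 9.1 sets N = 300 by reference to the ICH exposure guideline. It gives no effect size, SD, alpha or power, so there is no calculation to reproduce.

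**Illustration.** The documents name no ECG variable and give no ECG variability. These inputs are assumptions: a 60 ms change, a 1% rate (3 of 300), all 300 subjects evaluable, and an SD of change of 15 to 20 ms (10 ms added as a favourable case). The 60 ms shows the arithmetic and is not a proposed limit.

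1. Shift in the mean: 3 × 60 / 300 = 0.6 ms.
2. Standard error of the mean change, SD/√n: 15/√300 = 0.87 ms; 20/√300 = 1.15 ms.
3. Allowing for the spread that the three subjects add, SD² becomes SD² + 60² × 0.01 × 0.99 = SD² + 35.6. The standard errors are then 0.67, 0.93 and 1.21 ms at SD 10, 15 and 20 ms.
4. Power of a paired two-sided 5% test (normal approximation): 14.5%, 9.9% and 7.9% at SD 10, 15 and 20 ms.
5. Simulated three-visit ANOVA (2,000 runs, between-subject SD 18 ms assumed, change placed at the last visit): 6% to 10% with repeated measures, and below 0.1% if pairing is ignored. The plan does not say which model applies.
6. With 6 of 300 affected, the mean moves 6 × 60 / 300 = 1.2 ms and paired power is 16% to 36%.

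**What the planned maximum adds.** The simulation used 4,000 runs, an SD of change of 15 ms and a visit-level SD of 15 to 25 ms, all assumed.

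| Subjects changing by 60 ms | Visit maximum belongs to one of them | Maximum rises by more than 20 ms from Visit 1 |
|---|---|---|
| 3 of 300 | 66% to 99% | 31% to 79% |
| 1 of 300 | 33% to 85% | 15% to 43% |

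The maximum often carries a trace of such a change. It does not show how many subjects changed or by how much.

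**What a count would add.** At a true rate of 1%, the chance that at least one affected subject appears is 1 − 0.99^300 = 95.1%. With no cases, the one-sided 95% upper bound is 1 − 0.05^(1/300) = 0.99%. With 200 evaluable subjects (assumed), these become 86.6% and 1.49%.

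**The case against.** The strongest reply is that several stronger readings fail.

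- **That ECG is half of the primary endpoint.** This might be inferred by stopping after the words on adverse events and ECG. The sentence goes on to chemistry, hematology and urinalysis, so ECG is one of five.
- **That ECG is analysed by means alone.** SD, CV%, SEM, minimum and maximum are also planned.
- **That large individual changes would go unseen.** The documents do not support this. The adverse event definition in Section 5.1 is wide enough to take in a new ECG abnormality, adverse events are counted by subject, and the visit extremes give partial cover.
- **That a non-significant ANOVA would be taken as showing no ECG effect.** No decision rule in the plan says so.
- **That the test could not detect the example at all.** Its power is low, not zero, and the example rests on assumed inputs.

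These corrections stand, but none of them supplies the missing count. The adverse event route depends on someone judging the tracing. Section 5.1 names laboratory findings but not ECG, and physician review is stated only at Visit 1 (Section 4.1). Sections 4.2.2 and 4.2.6 say only that ECGs are recorded.

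It can also be said that the stakes are low. The Introduction describes lactitol as barely absorbed, with adverse events mostly gastrointestinal, and a single-arm study has no comparator for such counts. Both points are fair and limit the weight of this point. The same lack of a comparator applies to laboratory and vital-sign data, for which the plan still provides shift tables.

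**Conclusion.** The gap is real and modest. Followed as written, the plan would not report how many subjects had a large ECG change from their own baseline, while comparable subject-level displays are planned for laboratory and vital-sign data in the same section. This conclusion rests on the text alone.

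The size is illustrative. Under the assumptions stated (60 ms, 1%, 300 evaluable, SD of change 15 to 20 ms), the mean moves 0.6 ms against a standard error of about 0.87 to 1.15 ms, and a paired test would flag it about 8% to 10% of the time. Other inputs would change these figures but not the absence of the count. This is a worthwhile improvement to reporting. It does not show that the safety assessment fails, because extremes and adverse event reports may still bring individual cases to light.

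**What to change.** In the ECG paragraph of Section 9.3.2, add:

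1. Within-subject change from Visit 1 to Visit 2, to Visit 6 and to the worst on-treatment value, for each ECG variable, with n (%) of subjects beyond limits that the sponsor fixes before database lock. Name the ECG variables there, since the documents do not.
2. A listing of subjects with clinically significant ECGs.
3. Where the physician's interpretation is captured at Visits 2 and 6, a shift table of that interpretation from Visit 1 (normal; abnormal, not clinically significant; abnormal, clinically significant).

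Report the number of subjects with both a baseline and a post-baseline ECG as the denominator. Keep the descriptive statistics and the ANOVA.

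The cost is SAP wording and a few tables, with no new ECGs or visits. Items 1 and 2 use ECG data and clinical judgements to the extent that the eCRF holds them. Item 3 needs confirmation that the interpretation is recorded after Visit 1. If it is not, the shift table would need a change in data collection, and item 1 can go ahead without it.
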